3.3 Safety Plan

This study will be monitored by the Principal Investigator and in accordance with all FDA safety reporting requirements. AEs and SAEs will be reviewed on an ongoing basis to identify potential safety concerns.

The principal Investigator is required to notify his/her Institutional Review Board (IRB) of a serious adverse event according to institutional policy. Enrolled subjects will be evaluated clinically including vital signs and standard laboratory test assessment.

3.5 Statement of Compliance

The study will be conducted in compliance with this protocol, principles of International Conference on Harmonization (ICH), Good Clinical Practice (GCP), Declaration of Helsinki, and all applicable national and local regulations governing clinical studies.

4. SUBJECT SELECTION

4.1 Number of Subjects

The planned sample size is 60 subjects.

Proprietary Information of MD Anderson

4.2 Inclusion Criteria

Eligible subjects will be considered for inclusion in this study if they meet all of the following criteria:

1. Histologically confirmed CD20+ follicular lymphoma, grade 1, 2, or 3a or marginal zone lymphoma.
2. Have had no prior systemic treatment for lymphoma
3. Bi-dimensionally measurable disease, with at least one mass lesion \geq 2 cm in longest diameter by CT, PET/CT, and/or MRI.
4. In the opinion of the investigator would benefit from systemic therapy
5. Stage II, III, or IV disease
6. Must be \geq 18 years of age
7. Eastern Cooperative Oncology Group (ECOG) performance status \leq 2
8. Adequate hematologic function within 28 days prior to signing informed consent, including:
 - a. Absolute neutrophil count (ANC) \geq 1,000/mm³, independent of growth factor support
 - b. Platelet counts \geq 100,000/mm³ or \geq 50,000/mm³ if bone marrow involvement with lymphoma, independent of transfusion support in either situation
9. Adequate organ function, including:
 - a. Serum aspartate transaminase (AST) or alanine transaminase (ALT) $<$ 3 x upper limit of normal (ULN)
 - b. Creatinine clearance $>$ 30 ml/min calculated by modified Cockcroft-Gault formula.
 - c. Bilirubin $<$ 1.5 x ULN unless bilirubin is due to Gilbert's syndrome, documented liver involvement with lymphoma, or of non-hepatic origin, in which case bilirubin should not exceed 3g/dL.
 - d. Prothrombin time (PT)/international normalized ratio (INR) $<$ 1.5 x ULN and partial thromboplastin time (PTT) $<$ 1.5 x ULN
10. Must be able to adhere to the study visit schedule and other protocol requirements

Proprietary Information of MD Anderson

11. Women of childbearing potential and men who are sexually active must be practicing a highly effective method of birth control during and after the study (females of childbearing potential: must either completely abstain from heterosexual sexual conduct or must use 2 methods of reliable contraception, 1 highly effective [intrauterine device, birth control pills, hormonal patches, injections, vaginal rings, or implants] and at least 1 additional method [condom, diaphragm, cervical cap] of birth control. Reliable contraceptive methods must be started at least 4 weeks before lenalidomide. Males who are sexually active must be practicing complete abstinence or agree to a condom during sexual contact with a pregnant female or female of child bearing potential. Men must agree to not donate sperm during and after the study. For females, these restrictions apply at least 4 weeks before study treatment, during the period of therapy and for 1 month after the last dose of study drug. For males, these restrictions apply during the period of therapy and for 3 months after the last dose of study drug.
12. Women of childbearing potential must have a negative serum (beta-human chorionic gonadotropin [β -hCG]) pregnancy test at screening. Women who are pregnant or breastfeeding are ineligible for this study.
 - a. Females of reproductive potential must adhere to the scheduled pregnancy testing as required in the Revlimid REMS® program.
13. Sign (or their legally-acceptable representatives must sign) an informed consent document indicating that they understand the purpose of and procedures required for the study, including biomarkers, and are willing to participate in the study.
14. All study participants must be registered into the mandatory Revlimid REMS® program, and be willing and able to comply with the requirements of the REMS® program.

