4.3 Exclusion criteria

Subjects will be ineligible for this study if they meet any of the following criteria:

1. Known active central nervous system lymphoma or leptomeningeal disease, except subjects with a history of central nervous system lymphoma treated and in remission > 6 months.
2. Evidence of diffuse large B-cell transformation
3. Grade 3b FL

Proprietary Information of MD Anderson

4. Any prior history of other malignancy besides FL or marginal zone lymphoma, unless the patient has been free of disease for \geq 5 years and felt to be at low risk for recurrence by the treating physician, except:
 - a. Adequately treated non-melanoma skin cancer or lentigo maligna without evidence of disease.
 - b. Adequately treated cervical carcinoma in situ without evidence of disease.
5. Any life-threatening illness, medical condition, or organ system dysfunction which, in the investigator's opinion, could compromise the subject's safety, interfere with the absorption or metabolism of ibrutinib or lenalidomide capsules, or put the study outcomes at undue risk, including but not limited to:
 - a. Moderate to severe hepatic impairment (Child-Pugh classes B and C)
6. Known history of human immunodeficiency virus (HIV), or active Hepatitis C Virus, or active Hepatitis B Virus infection, or any uncontrolled active systemic infection
 - a. Patients with inactive hepatitis B infection must adhere to hepatitis B reactivation prophylaxis unless contraindicated.
7. Prior use of ibrutinib or other BTK inhibitors, rituximab or lenalidomide
8. Concurrent systemic immunosuppressant therapy (e.g., cyclosporine, tacrolimus, etc., or chronic administration glucocorticoid equivalent of >10 mg/day of prednisone) within 28 days of the first dose of study drug
9. Known anaphylaxis or IgE-mediated hypersensitivity to murine proteins or to any component of rituximab
10. Requires anticoagulation with warfarin or equivalent vitamin K antagonists (e.g., phenprocoumon). If patients have been on warfarin or equivalent vitamin K antagonists in the past, they will not be eligible if administered within 30 days of the first dose of study drug.
11. Requires chronic treatment with strong CYP3A inhibitors, for a list of strong CYP3A inhibitors, see Section 6.1.2.1. If patients have been on a strong CYP3A inhibitor in the past, they will not be eligible if the CYP3A inhibitor was administered within 7 days of the first dose of study drug.

Proprietary Information of MD Anderson

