13.4 Child Pugh Calculation

Clinical or laboratory characteristic	Points *		
	1	2	3
Albumin (g/dL)	>3.5g	2.8-3.5	<2.8
Total bilirubin (md/dL)	<2	2-3	>3
INR	<1.7	1.7-2.3	>2.3
Ascites	None	Mild/moderate (diuretic-responsive)	Severe (diuretic-refractory)
Encephalopathy	None	Grade 1-2 (precipitant-induced)	Grade 3-4 (chronic)

*Child-Pugh Score is obtained by adding the score for each parameter.

Child-Pugh Class:

A= 5-6 points

B= 7-9 points

C= 10-15 points

Proprietary Information of MD Anderson

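### The bilirubin cap for exempted patients in inclusion item 9c is printed in g/dL and cannot bind as written; exclusion 5a only partly covers the gap

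*Combined protocol and SAP*

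**What the plan says.** Section 4.2 requires every inclusion criterion to be met. Item 9c sets bilirubin below "1.5 x ULN unless bilirubin is due to Gilbert's syndrome, documented liver involvement with lymphoma, or of non-hepatic origin", and closes with the limit for those three groups: "in which case bilirubin should not exceed 3g/dL". No other section restates or corrects that unit.

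Appendix 13.4 is the only other place where bilirubin is put on an absolute scale. The row is headed "Total bilirubin (md/dL", with cut-points of less than 2, 2 to 3, and more than 3.

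Section 4.3, exclusion 5, covers illness or organ dysfunction that the investigator judges could endanger the patient, impair drug handling or put the study outcomes at risk. Its listed example, 5a, is "Moderate to severe hepatic impairment (Child-Pugh classes B and C").

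**The concern.** Item 9c is an operative eligibility threshold. For the three exempted groups it replaces the ordinary limit with one absolute number, and in the unit printed that number is out of physiological reach. Item 9c read alone therefore places no effective ceiling on the patients for whom the ordinary limit has been lifted.

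Two things are at stake. The first is patient selection: a literal reading admits any exempted patient on this criterion. The second is auditability. If staff silently read the limit as mg/dL, they enforce something the protocol does not state, and a deviation review has no usable written number to check against. A reader who turns to Appendix 13.4 to settle the matter finds no clean unit there either.

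**Working it through.** There is no calculated figure to reproduce here. The check is a unit conversion followed by scoring with the plan's own table.

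**Inputs**
- General limit: below 1.5 x ULN (Section 4.2, item 9c).
- Cap for the exempted groups: 3 g/dL (same item).
- Child-Pugh bilirubin points: 1 for less than 2, 2 for 2 to 3, 3 for more than 3. There are four other items, each scoring at least 1. Class A is 5 to 6 points, B is 7 to 9, C is 10 to 15 (Appendix 13.4).
- Bilirubin ULN: not given in the documents. Assumed range 1.0 to 1.5 mg/dL.
- Unit of the Appendix 13.4 scale: assumed to be mg/dL. Cut-points of 2 and 3 allow no other sensible reading, but this is an assumption.

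**Step 1: the cap as written**

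3 g/dL x 1000 mg/g = 3000 mg/dL.

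Against a value of 3 on the appendix scale: 3000 / 3 = 1000.

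**Step 2: the cap in multiples of ULN**

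| Assumed ULN (mg/dL) | General limit, 1.5 x ULN (mg/dL) | Cap as written / ULN | A value of 3 mg/dL / ULN |
|---|---|---|---|
| 1.0 | 1.5 | 3000 | 3.0 |
| 1.5 | 2.25 | 2000 | 2.0 |

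As written, the cap is 2000 to 3000 x ULN, against a general limit of 1.5 x ULN. On the appendix scale, a value of 3 would be 2.0 to 3.0 x ULN, a moderate relaxation of the general limit. That points to a unit slip. It does not establish what cap the sponsor intended.

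**Step 3: does another criterion catch these patients?**

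Minimum Child-Pugh total = 4 x 1 + bilirubin points.

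| Bilirubin on the appendix scale | Points | Minimum total | Lowest possible class |
|---|---|---|---|
| less than 2 | 1 | 4 + 1 = 5 | A |
| 2 to 3 | 2 | 4 + 2 = 6 | A |
| more than 3 | 3 | 4 + 3 = 7 | B |

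Any bilirubin above 3 on that scale therefore scores at least class B, a class that exclusion 5a names. The boundary is the same number that item 9c uses.

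**Step 4: how far that backstop reaches**

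Set beside item 9c, exclusion 5a falls short in three ways. It is an example under a criterion that turns on the investigator's opinion. It is about hepatic impairment, whereas item 9c expressly exempts bilirubin of non-hepatic origin and Gilbert's syndrome, and the protocol does not say whether such patients are to be scored and classed as hepatically impaired. And it depends on the Appendix 13.4 scale, whose unit is itself unclear.

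**Step 5: effect on the statistics**

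None. The precision statement in Section 9.5 follows from the sample size and expected rate alone: 1.96 x sqrt(0.77 x 0.23 / 60) = 0.106, as stated. The toxicity rule in Section 9.6 uses no bilirubin threshold.

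**The case against.** The strongest objection is that this is an obvious typographical slip with little practical effect. A limit of 3000 mg/dL is so implausible that staff would probably read it as mg/dL. The study has one center and eligibility is assessed by the investigator. No checklist or case report form is among the documents, so carry-over of the wrong unit cannot be shown. Only patients above the general limit for one of three reasons are affected, and the documents give no count of them. All of this stands, and it keeps the point small.

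A second objection is that exclusion 5a already stops patients with bilirubin above 3. This stands in part. A reader might infer from item 9c that exempted patients face no bilirubin limit anywhere in the protocol. The documents do not support that, because the Child-Pugh scoring leads any such value to a class that 5a names. What does not stand is that 5a makes the cap redundant, for the reasons in step 4 of the working.

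A third objection concerns the appendix unit. It differs from mg/dL by one letter, in a table read from PDF by a program, and the response table in Appendix 13.2 shows similar damaged characters. A reader might infer that the protocol itself misprints the unit in Appendix 13.4. The available text cannot establish that. The doubt weighs less on item 9c, where the limit stands in running text with a well-formed unit. Units elsewhere came through cleanly, such as creatinine in mg/dL (Appendix 13.3) and albumin in g/dL (Appendix 13.4).

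**Conclusion.** The point holds for item 9c: the cap for the exempted groups, as printed, is 3000 mg/dL and cannot bind. The factor of 1000 rests on reading the Appendix 13.4 scale as mg/dL. The multiples of ULN rest on an assumed ULN of 1.0 to 1.5 mg/dL.

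The consequence is limited. Exclusion 5a is a partial backstop that does not clearly cover Gilbert's syndrome or non-hepatic bilirubin. The point is about an eligibility criterion that should be applicable and auditable as written; it is not a flaw in the design or the analysis.

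**What to change.** - Correct the unit in Section 4.2, item 9c, and have the medical lead confirm the intended cap. This review takes no position on what the cap should be.
- Reconcile item 9c with Appendix 13.4 and exclusion 5a, and state whether patients with Gilbert's syndrome or non-hepatic bilirubin are to be scored by Child-Pugh for the purpose of 5a.
- Check the bilirubin unit in Appendix 13.4 against the source document and correct it if the fault is there. That table also determines which patients fall under Table 1 in Section 5.3.1, so its unit should be unambiguous.

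The cost is one unit correction, possibly a second, and a clarifying sentence. No data collection or analysis changes, since total bilirubin is already part of the screening chemistry in Section 7.1.

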4.3 Exclusion criteria

Subjects will be ineligible for this study if they meet any of the following criteria:

1. Known active central nervous system lymphoma or leptomeningeal disease, except subjects with a history of central nervous system lymphoma treated and in remission > 6 months.
2. Evidence of diffuse large B-cell transformation
3. Grade 3b FL

Proprietary Information of MD Anderson

4. Any prior history of other malignancy besides FL or marginal zone lymphoma, unless the patient has been free of disease for \geq 5 years and felt to be at low risk for recurrence by the treating physician, except:
 - a. Adequately treated non-melanoma skin cancer or lentigo maligna without evidence of disease.
 - b. Adequately treated cervical carcinoma in situ without evidence of disease.
5. Any life-threatening illness, medical condition, or organ system dysfunction which, in the investigator's opinion, could compromise the subject's safety, interfere with the absorption or metabolism of ibrutinib or lenalidomide capsules, or put the study outcomes at undue risk, including but not limited to:
 - a. Moderate to severe hepatic impairment (Child-Pugh classes B and C)
6. Known history of human immunodeficiency virus (HIV), or active Hepatitis C Virus, or active Hepatitis B Virus infection, or any uncontrolled active systemic infection
 - a. Patients with inactive hepatitis B infection must adhere to hepatitis B reactivation prophylaxis unless contraindicated.
7. Prior use of ibrutinib or other BTK inhibitors, rituximab or lenalidomide
8. Concurrent systemic immunosuppressant therapy (e.g., cyclosporine, tacrolimus, etc., or chronic administration glucocorticoid equivalent of >10 mg/day of prednisone) within 28 days of the first dose of study drug
9. Known anaphylaxis or IgE-mediated hypersensitivity to murine proteins or to any component of rituximab
10. Requires anticoagulation with warfarin or equivalent vitamin K antagonists (e.g., phenprocoumon). If patients have been on warfarin or equivalent vitamin K antagonists in the past, they will not be eligible if administered within 30 days of the first dose of study drug.
11. Requires chronic treatment with strong CYP3A inhibitors, for a list of strong CYP3A inhibitors, see Section 6.1.2.1. If patients have been on a strong CYP3A inhibitor in the past, they will not be eligible if the CYP3A inhibitor was administered within 7 days of the first dose of study drug.

Proprietary Information of MD Anderson

12. Requires chronic treatment with strong CYP3A inducers, for a list of strong CYP3A inducers, see Section 6.1.2.1. If patients have been on a strong CYP3A inducer in the past, they will not be eligible if the CYP3A inducer was administered within 7 days of the first dose of study drug.
13. Clinically significant cardiovascular disease such as uncontrolled or symptomatic arrhythmias, congestive heart failure, or myocardial infarction within 6 months of Screening, or any Class 3 (moderate) or Class 4 (severe) cardiac disease as defined by the New York Heart Association Functional Classification.
14. Significant screening electrocardiogram (ECG) abnormalities including left bundle branch block, 2nd degree atrioventricular (AV) block, type II AV block, or 3rd degree block.
15. Known bleeding diathesis (e.g., von Willebrand's disease) or hemophilia
16. History of stroke or intracranial hemorrhage within 6 months prior to study entry.
17. Vaccinated with live, attenuated vaccines within 4 weeks of study entry
18. Lactating or pregnant subjects
19. Administration of any investigational agent within 28 days of first dose of study drug.
20. Patients who have undergone major surgery within 7 days or minor surgery within 3 days of first dose of study drug.

5. **TREATMENT OF SUBJECTS**

5.1 **Enrollment and Blinding**

This is an open-label, phase 2 study with one treatment arm. Subjects will not be blinded to study drug nor will they be randomized. Enrolled subjects will receive open-label capsules of ibrutinib and lenalidomide in combination with IV rituximab.

5.2 **Formulation, Packaging and Storage**

5.2.1 **Ibrutinib**

Ibrutinib capsules are provided as a hard gelatin capsule containing 140mg of ibrutinib. The ibrutinib capsules will be packaged in opaque high-density polyethylene plastic bottle with labels bearing the appropriate label text as required by governing regulatory agencies. Study drug will be dispensed in child-resistant packaging.

Proprietary Information of MD Anderson

At the study site, all investigational study drugs will be stored at room temperature in a locked, safe area to prevent unauthorized access. Ibrutinib will be provided by Janssen Scientific Affairs, LLC to research subjects for the duration of their participation in this trial at no charge to them or their insurance providers. Additional prescribing information can be found at www.imbruvica.com

5.2.2 Rituximab

Commercially available rituximab will be used. Rituximab is a sterile, clear, colorless, preservative-free liquid concentrate for IV administration. Rituximab is supplied at a concentration of 10mg/mL in either 100mg (10mL) or 500mg (50mL) single-use vials. The product is formulated for IV administration in 9.0mg/mL sodium chloride, 7.35mg/mL sodium citrate dehydrate, 0.7mg/mL polysorbate 80, and Sterile Water for Injection. The pH is adjusted to 6.5. Rituximab vials should be stored refrigerated between 2° to 8°C (36° to 46°F). Vials should be protected from the light. Additional prescribing information can be found at www.gene.com/download/pdf/rituxan_prescribing.pdf

5.2.3 Lenalidomide

Lenalidomide (Revlimid®) will be provided to research subjects for the duration of their participation in this trial at no charge to them or their insurance providers. Lenalidomide will be provided in accordance with the Celgene Corporation's Revlimid REMS® program. Per standard Revlimid REMS® program requirements, all physicians who prescribe lenalidomide for research subjects enrolled into this trial, and all research subjects enrolled into this trial, must be registered in, and must comply with, all requirements of the Revlimid REMS® program.

Drug will be shipped on a per patient basis by the contract pharmacy to the clinic site for IND studies. Only enough lenalidomide for one cycle of therapy will be supplied to the patient each cycle.

Lenalidomide is available in capsule doses of 2.5mg, 5mg, 10mg, 15mg, 20mg, and 25mg. Lenalidomide should be stored as directed on the respective package labels. Lenalidomide should be stored at room temperature away from direct sunlight and protected from excessive heat and cold. Additional prescribing information can be found at www.revlimid.com/wp-content/uploads/2013/11/PI.pdf

5.3 Treatment Schedule

Patients will receive 12 cycles of lenalidomide, 15mg daily on days 1-21 of cycle 1, and 20mg daily on days 1-21 (± 2 days) of cycles 2 through 12. Cycles will be 28 days in length. Patients will receive rituximab, 375mg/m² on days 1, 8 (± 2 days), 15 (± 2 days), and 22 (± 2 days) of cycle 1, and day 1 (± 2 days) of cycles 2 through 12. Patients will receive ibrutinib 560mg daily, starting on day 1 of cycle 1 and continued through 12 cycles. Therapy is continued for 12 cycles or until disease progression, unacceptable toxicity, or voluntary withdrawal.

5.3.1 Dosage and Administration

Below are specific administration instructions for drugs used within this study:

Proprietary Information of MD Anderson

Ibrutinib

Ibrutinib 560mg (4 x 140mg capsules) is administered orally once daily with approximately 8 ounces (240mL) of water. Ibrutinib may be administered with or without food. For patients with mild liver impairment (Child-Pugh Class A), the recommended dose of ibrutinib is 140 mg daily (one capsule), see Table 1. Grapefruit or Seville oranges should be avoided due to CYP3A4/5 inhibition. Capsules should be swallowed intact and subjects should not attempt to open, break or chew the capsules or dissolve in water. Capsules should be taken at approximately the same time each day. No extra capsules should be taken to make up missed doses of ibrutinib. Ibrutinib dosing is continuous throughout the treatment phase. If a dose is missed, it can be taken as soon as possible on the same day with a return to the normal schedule the following day. No extra capsules to make up the missed dose should be taken.

Table 1. Ibrutinib Dose Adjustment for Patients with Hepatic Impairment

Category	Hepatic Impairment (Child-Pugh)	Dose
Mild hepatic impairment	Class A	140mg (1 capsule) daily

Ibrutinib will be dispensed to subjects in bottles. Unused ibrutinib capsules dispensed during the previous visits should be returned and accountability records must be updated. Unused capsules should not be re-distributed to anyone. Subjects should return all used bottles to the site when they receive new study drug. Unused study drug will be destroyed as per our institution guidelines.

Treatment will continue until disease progression, end of study, or other reason for treatment discontinuation outlined in section 8. Dose modifications for toxicity are outlined in section 5.4.

Rituximab

Rituximab is given as 375mg/m² IV infusion once weekly for 4 doses starting on day 1 of cycle 1 (\pm 2 days). For cycles 2 through 12, rituximab is given as 375mg/m², one dose on day 1 (\pm 2 days) of each cycle. The costs for administering rituximab are to be covered by the individual subject's insurance. Pre medications for rituximab will be administered per institutional guidelines.

First infusion:

Rituximab should be administered intravenously per institutional guidelines. The final concentration of rituximab is 1mg/mL. Rituximab will be administered at an initial rate of 50mL/hr. The infusion rate may be escalated in 50mL/hr increments every 30 minutes to a maximum of 400mL/hr as tolerated. If hypersensitivity or an infusion reaction develops, the infusion should be interrupted until symptoms resolve or improve. For management of infusion reaction, please refer to the institution's

Proprietary Information of MD Anderson

hypersensitivity reaction order sheet. The infusion can continue at one-half the previous rate upon improvement in symptoms, and the escalation of 50mL/hr increments every 30 minutes resumes to a maximum rate of 400mL/hr.

Subsequent infusions:

If subjects tolerated the first infusion well, the subsequent infusions can start at an initial rate of 100mL/hr as per institution guidelines and increase by 100mL/hr increments every 30 minutes to a maximum of 400mL/hr as tolerated. If subjects did not tolerate the first infusion well, follow the guidelines for the first infusion.

Lenalidomide

Patients with CrCl >60 mL/min will receive 15mg of lenalidomide days 1 through 21 of cycle 1, and 20mg of lenalidomide days 1 (\pm 2 days) through 21 every 28 day days for cycles 2 through 12 for a total of 12 cycles. Dosing will be based on patient's creatinine clearance (CrCL) as calculated by modified Cockcroft-Gault (Appendix 13.3), Table 2. See below for further instruction on dose adjustment for subjects with renal impairment.

Lenalidomide should be taken orally at about the same time each day, either with or without food. Lenalidomide capsules should be swallowed whole with water, and should not be opened, broken, or chewed. If a dose is missed, it can be taken as soon as possible on the same day with a return to the normal schedule the following day. No extra capsules to make up the missed dose should be taken. Females of childbearing potential should not handle or administer lenalidomide unless they are wearing gloves. Unused lenalidomide capsules dispensed during the previous visits should be returned and accountability records must be updated. Unused capsules should not be re-distributed to anyone. Subjects should return all used bottles to the site when they receive new study drug. Unused study drug will be destroyed as per our institution guidelines.

Lenalidomide Dose Adjustment for Renal Impairment

Subjects with renal impairment (CrCl \leq 60 ml/min) will be dosed based on Table 2. CrCL assessment will occur on: Day 1, 8, 15, and 22 for cycle 1; Day 1 and 15 for cycle 2; Day 1 of cycles 3-12. However, if a subject has a creatinine obtained at any time during the Treatment Phase because it was clinically indicated, a dose reduction based on CrCL and Table 2 should be performed. For cycle 1, subjects with renal impairment, CrCl of 30-60mL/min, will initiate 15mg of lenalidomide every 48 hours. Subjects with renal impairment, CrCL of <30 mL/min prior to cycle 1, will initiate 10mg of lenalidomide every 48 hours. For subjects with renal impairment (CrCl \leq 60 ml/min) necessitating dose adjustment on Day 1 of a cycle according to Table 2, but then stably improves, a dose increase based on CrCL will not occur until day 1 of the next cycle. For subjects with CrCl \leq 60 ml/min at study initiation, but then stably improves to $>$ 60 ml/min, proceed to lenalidomide 20 mg once daily with Cycle 2. At any point, should a patient

Proprietary Information of MD Anderson

require dose reduction due to reduced CrCl, and the CrCl then stably improves, dose escalation will not occur until day 1 of the next cycle.

Table 2. Lenalidomide Dose Adjustment for Patients with Renal Impairment

Category	Renal Function (modified Cockcroft-Gault)	Cycle 1	Cycle 2 onward
Mild or no renal impairment	CrCl > 60 mL/min	15 mg once daily	20 mg once daily
Moderate renal impairment	CrCl 30-60 mL/min	15 mg every 48 hours	10mg every 24 hours *
Severe renal impairment	CrCl <30mL/min (not requiring dialysis)	10 mg every 48 hours	15mg every 48 hours *

* If CrCl is \leq 60 mL/min at study initiation but then stably improves to >60 mL/min, proceed to lenalidomide 20 mg once daily with Cycle 2.

